### 10.3. Appendix 3: Assessment Windows

In general, data will be reported according to the nominal time of clinic visits and assessments as specified in the protocol. For example, if a participant has values recorded for the Week 4 visit that were actually made on the 23rd day of treatment, they will be presented as Week 4 values in the summary tables.

The post-randomization study data collected at early withdrawal (EW) visits in the eCRF and SDTM data will be mapped based on study day as follows:

Study days	Target date for visit	Visit/Week
15 to 56	29	Visit 3/ Week 4
57 to 126	85	Visit 4/ Week 12
>=127	169	Visit 5/Week 24

Note:

- For 3 hrs post-dose FEV1 there are no planned assessments at weeks 4 and 12, and so data that slots to weeks 4 and 12 will be excluded from summaries and analyses.

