#### 7.1.5.1. Statistical Methodology Specification

Endpoint / Variables

Mean change from baseline in trough FEV1 at Week 24

Model Specification

FEV1 and change from baseline will be summarized at each visit according to treatment status (on-treatment or post-treatment). Baseline FEV1 will be summarized overall and split by participants who have an on-treatment FEV1 value at week 24, participants who have a post-treatment FEV1 value at week 24 and participants with missing FEV1 data at Week 24.

The primary efficacy analysis will evaluate the treatment policy (de facto) type estimand in the ITT population, using a MMRM analysis.

Analyses will include the fixed, categorical effects of treatment, visit, treatment by visit interaction, sex, region, as well as continuous fixed covariates of age, baseline value and baseline value by visit interaction. Point estimates and 95% confidence intervals will be calculated for the primary comparisons of interest. See details in Section 2.4

- Clinic trough FEV1 data (both on- and post-treatment) collected at all scheduled clinic visits will be included in the analysis. These include the clinic visits at Weeks 4, 12 and 24.
- While missing data are not explicitly imputed in the MMRM analyses, there is an underlying assumption that any missing data are missing at random. All available data will be utilized via modelling of the within-participant correlation structure, the derived treatment differences will be adjusted to take into account the missing data.

Terms in the model:

- Dependent Variable: change from baseline in trough FEV1 at each visit
- Covariates:
  - Categorical: treatment group, sex, region, visit
  - Continuous: age, baseline value for clinic FEV1
  - Interaction: baseline\*Visit, treatment\*Visit
- Repeated: Visit
- The model will be fitted with an unstructured variance-covariance matrix.
- The OM option in SAS will be used to derive the LS means based on the distribution of the covariates observed in the data.
- Baseline is defined in Section 5.2.1
- Two models will be fitted; one with a response variable of change from baseline and one with the response variable as the raw value.

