### 8.6.2. ECG

12-lead ECGs are measured at Visit 1, and approximately 15-45 minutes after the administration of study treatment at Visits 3 and 5, and at Early Withdrawal visit. The ECG measurements of interest are QTc (F), heart rate, and PR interval. QTc(B) will also be summarized. All ECG data present in the database will be considered valid and will be reported (even if the ECG had a technical error).

For a given participant, the baseline value for each of the parameters is the last value recorded prior to randomized treatment start date, generally the assessment at Visit 1, but can be a repeat and/or unscheduled assessment. Change from baseline value at post-randomization visit is the difference between the first recorded ECG value at the clinic visit and the baseline value.

The ‘maximum/minimum post-baseline’ value will be derived as the maximum/minimum on-treatment value recorded at any scheduled, unscheduled, or Early Withdrawal (EW) visit after the start of study treatment. QTc (F) values (including ‘maximum post-baseline’) will be categorized as follows:  $\leq 450\text{msec}$ ,  $>450$  to  $\leq 480\text{msec}$ ,  $>480$  to  $\leq 500\text{msec}$ ,  $>500$  to  $\leq 530\text{msec}$  and  $>530\text{msec}$ . Change from baseline QTc (F) values (including change to ‘maximum post baseline’) will be categorized as follows:  $\leq -60\text{msec}$ ,  $>-60$  to  $\leq -30\text{msec}$ ,  $>-30$  to  $\leq 0\text{msec}$ ,  $>0$  to  $\leq 30\text{msec}$ ,  $>30$  to  $\leq 60\text{msec}$ , and  $>60\text{msec}$ .

See Section 8.6.4 for details on the statistical analysis of QTc (F) and PR interval data.

An ‘any time post-baseline’ ECG interpretation will be derived as the worst on-treatment interpretation recorded at a scheduled, unscheduled, or EW visit after the start of study treatment. The worst case post-baseline is defined as:

- ‘Abnormal’ if any on-treatment assessment is evaluated as ‘Abnormal’
- ‘Unable to evaluate’ if all on-treatment assessments are ‘Unable to evaluate’
- ‘Normal’ if any on-treatment assessment is evaluated as ‘Normal’ and there are no on-treatment assessments evaluated as ‘Abnormal’

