#### 8.6.4. Planned Statistical Analyses of Safety Endpoints

Statistical Analysis of Safety Endpoints	
Endpoints	

• Change from baseline in Systolic BP

• Change from baseline in Diastolic BP

• Change from baseline in Pulse rate

• Change from baseline in PR interval;

• Change from baseline in QTc (F) interval

	
Model Specification, Checking, Results Presentation and SAS code	

• These endpoints will be analyzed using the same methodology as for the primary analysis of trough FEV1 as outlined in Section 7.1.

• All on-treatment data collected at scheduled clinic visits will be included.

	

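### Early-withdrawal ECGs from Days 57–126 slot to Week 12, where no ECG is planned, and can enter the ECG summaries and the PR and QTc(F) models as a sparse visit of early stoppers only

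*SAP*

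**What the plan says.** - **When ECGs are taken.** Section 8.6.2 places the post-randomization ECGs "after the administration of study treatment at Visits 3 and 5, and at Early Withdrawal visit". The schedule in Section 10.2.1 agrees: there is none at Visit 4 (Week 12).
- **How EW data are slotted.** Section 10.3: "The post-randomization study data collected at early withdrawal (EW) visits in the eCRF and SDTM data will be mapped based on study day as follows". Days 15–56 go to Week 4, Days 57–126 to Week 12, and Day 127 onwards to Week 24. The rule is not limited by type of assessment.
- **The only exception.** The note under that table says that 3-hour post-dose FEV1 has no planned assessment at Weeks 4 and 12, "and so data that slots to weeks 4 and 12 will be excluded from summaries and analyses". ECG is not named.
- **The models.** For blood pressure, pulse rate, PR and QTc(F), Section 8.6.4 says "These endpoints will be analyzed using the same methodology as for the primary analysis of trough" FEV1. Section 7.1.5.1 defines that analysis with visit, treatment-by-visit and baseline-by-visit terms, and adds: "The model will be fitted with an unstructured variance-covariance matrix".
- **The data entering the models.** Section 8.6.4: "All on-treatment data collected at scheduled clinic visits will be included". Section 8 sets the same limit for the by-visit safety summaries.

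**The concern.** ECG at Week 12 has the gap that the Section 10.3 note closes for 3-hour FEV1, but the note leaves ECG out. Trough spirometry, the questionnaires and vital signs are all planned at Week 12, so an EW value slotted there joins values from participants who attended Visit 4. An EW ECG slotted there joins nothing, because the whole Week 12 row would be people who were stopping.

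Two things are at stake. The by-visit ECG tables could show a Week 12 mean per arm that looks like a planned time point but describes only early stoppers. The PR and QTc(F) models could also acquire a third visit that no participant shares with Week 24, so that one element of the unstructured matrix has no data behind it. ECG measurements are a named safety endpoint in Section 2.2.

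**Working it through.** The SAP states no figure on this point, so there is none to reproduce. The check has four steps.

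**1. Can EW ECGs enter as Week 12?** The wording on scheduled visits pulls both ways.

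- *Towards entry.* Section 10.4.1 counts the EW visit as a possible last scheduled clinic visit. Section 7.1.5.1 uses the same scheduled-visit limit for trough FEV1; if that limit kept slotted EW data out, the slotting table would do nothing for the primary endpoint. The 3-hour FEV1 note is needed only if slotted EW data would otherwise be used. Section 10.3 gives the scheduled measurement priority within a window, and for a Week 12 ECG there is never one to take priority. Section 8.6.4 also imports the results presentation of Section 7.1.5.1, which asks for differences at Weeks 4, 12 and 24.
- *Against entry.* Section 8.6.2 lists scheduled, unscheduled and EW visits as separate kinds, and Section 10.6.1 excludes EW from scheduled visits when deciding who continues in the study.

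So entry is possible but not certain.

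**2. How many people?** Input: Section 5.4 gives 174 + 69 + 21 + 114 + 58 = 436 randomized. Assumptions, none from the SAP: a proportion *d* withdraws, evenly over Days 1–169; a proportion *f* of those has an on-treatment EW ECG. The window covers 126 − 57 + 1 = 70 days.

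Expected total = 436 × *d* × (70/169) × *f*; per arm, λ = total/3. With Poisson counts, P(at least one arm empty) = 1 − (1 − e^−λ)³.

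| *d* | *f* | Total | Per arm | P(some arm empty) |
|---|---|---|---|---|
| 3% | 50% | 2.7 | 0.9 | 0.79 |
| 5% | 100% | 9.0 | 3.0 | 0.14 |
| 10% | 100% | 18.1 | 6.0 | 0.007 |
| 15% | 100% | 27.1 | 9.0 | <0.001 |

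The range is about 3–27 people in total, or 1–9 per arm.

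**3. What happens to the covariance?** Only on-treatment ECGs count. Someone whose on-treatment EW ECG falls on Days 57–126 cannot also have an on-treatment Week 24 ECG. With three visits the unstructured matrix has 3 × 4/2 = 6 parameters, and no participant informs cov(Week 12, Week 24).

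This was checked on simulated data: 436 participants, SD 15 msec, correlation 0.6, 9 people with Weeks 4 and 12 only (3 per arm), 10 with Week 4 only, 5 with Week 24 only, and the rest with Weeks 4 and 24. The −2 REML value was 5265.621352 at every Week 12–Week 24 correlation tried (−0.2, 0, 0.3, 0.6, 0.9). The Hessian row for that covariance was zero, so 1 of the 6 parameters is not identified.

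**4. What happens to the contrasts?** In the same simulation, with the other covariance parameters held at their assumed values, the SEs of a treatment difference were 1.77 msec at Week 4, 9.88 at Week 12 and 1.79 at Week 24, whatever value the unidentified covariance took. The Week 12 SE is 9.88/1.79 ≈ 5.5 times the Week 24 SE.

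A hand check agrees. At Week 12, given Week 4, the variance is 225 × (1 − 0.6²) = 144, and √(2 × 144/3) = 9.8. At Week 4, 436 − 5 = 431 people give about 143.7 per arm, and √(2 × 225/143.7) = 1.77. If an arm has no Week 12 value, its Week 12 least-squares mean is not estimable.

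**The case against.** The strongest reply is that Sections 8 and 8.6.4 already restrict the data to scheduled clinic visits, and that the ECG section itself treats EW as a separate kind of visit. Section 10.3 also opens by reporting data at protocol-specified times, and none is specified for a Week 12 ECG. On that reading nothing enters. This is a fair reading, but not the only one, for the reasons in step 1 of the working. It reduces the point from a certainty to a possibility that the text leaves open.

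The second reply is that few ECGs qualify. An ECG counts as on-treatment only up to one day after the treatment stop date (Section 10.4.1). Participants who stop treatment are encouraged to stay in the study, and if they withdraw later their EW ECG is post-treatment. This stands. It argues for a small count, which limits the damage but also makes any Week 12 row harder to interpret.

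A reader might go further and infer that the PR and QTc(F) models cannot be fitted, that Kenward-Roger must fail, and that a new covariance structure would then be picked after unblinding. The documents do not support this. The unidentified covariance does not enter the likelihood, the contrasts at the planned weeks do not depend on it, and software may still return a fit. No Kenward-Roger fit was run here. For a Kenward-Roger failure, Section 7.1.5.1 has a fixed fallback, the residual method; the open choice of structure, guided by AIC, applies only to non-convergence.

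**Conclusion.** The point holds in limited form. As written, the slotting rule can put a Week 12 visit made up only of early stoppers into the by-visit ECG summaries and the PR and QTc(F) models. Whether it does depends on whether EW counts as a scheduled clinic visit, on which Section 10.4.1 differs from Sections 8.6.2 and 10.6.1.

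The size is modest. The count of about 3–27 rests on assumed withdrawal of 3–15%, even timing, and 50–100% of withdrawers having an on-treatment ECG. The SE ratio of about 5.5 rests on 3 Week 12 values per arm, SD 15 msec and correlation 0.6. The Week 4 and Week 24 contrasts are essentially unaffected, and the primary endpoint is not touched. This is a minor correction to a safety analysis, worth making because the SAP already applies the same remedy to 3-hour FEV1.

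**What to change.** Extend the note in Section 10.3 to ECG: no ECG is planned at Week 12, so EW ECGs that slot there are left out of the by-visit summaries and of the PR and QTc(F) models, but stay in the maximum/minimum and any-time post-baseline displays and in the listings.

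State in Section 8.6.4 that the ECG models use Weeks 4 and 24 only. The unstructured matrix then has 2 × 3/2 = 3 parameters, all informed by participants seen at both visits, and no Week 12 ECG contrast is requested.

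It would also help to say once whether EW counts as a scheduled clinic visit for analysis purposes, so that Sections 8.6.2, 10.4.1 and 10.6.1 agree.

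The cost is a sentence in each of two sections and one programming filter. No tracing is lost, because the worst-case displays in Section 8.6.2 already take in on-treatment EW values.

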#### Multiple assessments slotting to the same visit

If there is more than one non-missing value within an assessment window for a given analysis or summary, the measure from the scheduled visit will take priority.

All data will be listed.

## 10.4. Appendix 4: Study Phases

### 10.4.1. Study Phases

Study phases for assessments scheduled at a set time will be defined according to the planned relative time of the assessment.

Any events/assessments for participants not in the ITT population will be assigned a Pre-treatment phase.

For all events and assessments, the study phases will be defined as follows:

Study Phase	Definition
Screening/Run-In period	Visit 1 date ≤ Assessment Date/Time < Date of randomization or randomized treatment start date, whichever is later.
On-Treatment during the Study	Randomized Treatment Start Date ≤ Event Onset Date or Assessment Date/Time ≤ Study Treatment Stop Date +1 day or any assessment with a missing or partial date unless there is evidence it was not on-treatment
Post-Treatment during the Study*	Randomized Treatment Stop Date +1 < Event Onset Date or Assessment Date/Time ≤ Last Scheduled Clinic Visit (i.e., Visit 5 (EOS Visit) or Early Withdrawal [EW] Visit) Note: if any participant does not receive a dose of randomized treatment then all post baseline data prior to early withdrawal or EOS visit is considered as post-treatment.
Post-Study	Event Onset Date > Last Scheduled Clinic Visit (i.e., Visit 5 (EOS Visit) or Early Withdrawal Visit) +1 day Note, for participants who continue in the study after IP discontinuation (i.e. where treatment discontinuation date < Visit 5 (EOS visit) date or EW visit date), the rule will be: Event Onset Date > Last Scheduled Clinic Visit (i.e. Visit 5 (EOS Visit) or EW Visit)

\*Only applicable for participants who continue in the study after IP discontinuation

Classification of a concomitant medication into study phases (pre-study period [at study entry], screening/run-in period, on-treatment during the study, post-treatment during the study, or post-study) will be made with reference to the study phase as defined above. A medication will be classified into every period in which it was taken. For medications with partial start and stop dates, the medication will be classified into every period in which it could have been taken.

## 10.5. Appendix 5: Data Display Standards & Handling Conventions

### 10.5.1. Reporting Process

Software	

 
The currently supported versions of SAS software will be used.
 
	
Reporting Area	
HARP Server	: UK1SALX00175
HARP Compound	: /arenv/arprod/gsk2834425/mid205832/final
QC Spreadsheet	: /arenv/arwork/gsk2834425/mid205832/final/documents
Analysis Datasets	

 
Analysis datasets will be created according to CDISC standards (SDTM Implementation Guide Version 3.1.3 or higher & ADaM Implementation Guide Version 1.0 or higher.
 
For creation of ADaM datasets (ADCM/ADAE), the same version of dictionary datasets will be implemented for conversion from SI to SDTM.
 
	
Generation of RTF Files	

 
Rich Text Format (RTF) files will be generated for the final reporting efforts to be used for the CSR writing.
 
	

### 10.5.2. Reporting Standards

General	

 
The current GSK Integrated Data Standards Library (IDSL) will be applied for reporting, unless otherwise stated: 
 
4.03 to 4.23: General Principles
 
5.01 to 5.08: Principles Related to Data Listings
 
6.01 to 6.11: Principles Related to Summary Tables
 
7.01 to 7.13: Principles Related to Graphics
 
 
 
Displays will use the term "Subjects" to refer to "Participants".
 
	
Formats	
	
 
All data (including data collected post treatment discontinuation) will be reported according to the treatment to which the participant was randomized unless otherwise stated. However, there may be additional adhoc displays for individual participants using the actual treatment received.
 
The reported precision of data will follow IDSL statistical principles but may be adjusted to a clinically interpretable number of decimal places.
 
In most cases, percentages between 1% and 99%, inclusive, will be rounded to integers. Percentages greater than 0%, but less than 1%, will be reported as <1%, and percentages greater than 99%, but less than 100%, will be reported as >99%. For some rare events, percentages may be reported in 1 decimal point. In this case, percentages greater than 0%, but less than 0.1%, will be reported as <0.1%.
 
Numeric data will be reported at the precision collected on the eCRF.
 
The reported precision from non eCRF sources will follow the IDSL statistical principles but may be adjusted to a clinically interpretable number of DP's.
 

Planned and Actual Time	


• Reporting for tables, figures and formal statistical analyses:

• Planned time relative to dosing will be used in figures, summaries, statistical analyses and calculation of any derived parameters, unless otherwise stated.

• If an assessment is reported for a scheduled visit regardless of assessment date/time relative to protocol T&E, the data will be used for that visit.

• Reporting for Data Listings:

• Planned and actual time relative to study drug dosing will be shown in listings (Refer to IDSL Statistical Principle 5.05.1).

• Unscheduled or unplanned readings will be presented within the participant's listings.

	
Unscheduled Visits	

• Unscheduled visits will not be included in summary tables and/or figures except as part of a 'worst case post-baseline' assessment.

• All unscheduled visits will be included in listings.

• Unscheduled visits may be used for baseline where specified.

	
Descriptive Summary Statistics	
Continuous Data	Refer to IDSL Statistical Principle 6.06.1
Categorical Data	N, n, frequency, %
Graphical Displays	

• Refer to IDSL Statistical Principles 7.01 to 7.13.

	

## 10.6. Appendix 6: Derived and Transformed Data

### 10.6.1. General

Study Day

Calculated as the number of days from randomization date:

Reference Date = Missing → Study Day = Missing

Reference Date < Treatment Start Date → Study Day = Reference Date – Treatment Start Date

Reference Date ≥ Treatment Start Date → Study Day = Reference Date – Treatment Start + 1

Treatment Period Completion/Withdrawal and Study Completion/Withdrawal


A participant is considered to have completed the treatment period if the answer to the question "Was the study treatment stopped permanently before the scheduled end of the treatment period?" on the Study Treatment Discontinuation eCRF page is "No". Date of completion of treatment period will be the treatment stop date.

A participant is considered to have completed the study if the answer to the question "Was the subject withdrawn from the study?" on the Study Conclusion eCRF page is "No". Otherwise, if the answer is "Yes" then the participant is considered to have withdrawn early from study. The date of study completion/withdrawal as entered on the eCRF will be used as the study completion/withdrawal date.

If a participant prematurely discontinues IP, according to the CRF instructions participants should be reported as continuing in the study if they attend either normal visits, or the safety follow-up visit after the early withdrawal visit (DSCONT='Y'). To identify participants who are continuing in the study per the normal visit schedule and providing post-treatment data, the following will be implemented:

If a participant prematurely discontinues IP and study at the same time, they are not considered to be continuing in the study (i.e. DSCONT will be "N").

If a participant prematurely discontinues IP and only has an EW visit and a safety follow up visit on or after the date of IP discontinuation they are not considered to be continuing in the study (DSCONT will be "Y"). Note, if a participant initially continues in the study following IP discontinuation but then discontinues study prior to the next scheduled clinic visit they will be considered as not continuing in the study as they will not be providing post-treatment data.

If a participant prematurely discontinues IP and has a scheduled visit (not EW or safety follow-up visit) on or after the date of IP discontinuation then the participant is continuing in the study (DSCONT will be "Y").

**Planned and Actual Treatment**

For participants who received the correct treatment throughout the study, the actual treatment will be the same as the planned treatment. For participants who received an incorrect treatment, the actual treatment will be derived as follows:

- If the number of doses on an incorrect treatment is less than the number of doses on the planned treatment then the actual treatment is assigned as planned treatment.
- If the number of doses on an incorrect treatment is greater than the number of doses on the planned treatment then the actual treatment is assigned as the incorrect treatment.
- If the number of doses on an incorrect treatment and planned treatment are the same, the actual treatment is assigned as the treatment with the highest UMEC dose.

Note: If any container (correct or incorrect) was dispensed and not returned, such that it is not possible to ascertain whether or not any doses were taken from the incorrect container, it will be assumed that the participant took all 30 possible doses from this container.

**Participants excluded from ITT population**

- A participant who is recorded as a screen failure or run-in failure but is randomized and does not receive a dose of study treatment, is considered to be randomized in error and will be excluded from the ITT population
- These participants will be identified using the deviations dataset where the term "Randomized in Error:" is reported.

